**Learning and its Neural Correlates During IBT.** Impairments in learning during IBT may hinder an individual's ability to benefit from it. As part of our open trial of IBT on DMDD, we gathered preliminary evidence suggesting that the clinician-rated degree of improvement in irritability in youths with DMDD trended towards an association with the overall change towards more positive, i.e. "happy," judgments over the course of IBT ( $r=.49$ ,  $p=.08$ ). Thus, the effect of IBT on irritability may be moderated or mediated by a patient's ability to learn new valence associations to ambiguous facial expressions, i.e. capacity to train against their hostile interpretation bias. As described in the preliminary studies section below, we have evidence that youths with severe irritability are slower learners during IBT. As a first step towards investigating the role of the threat-learning system as a mediator of IBT treatment effect on irritability, we will test the hypothesis that pre-IBT irritability is associated with deficits in a person's ability to learn benign associations (hypothesis 2.1).

Learning during IBT should involve the neural threat-learning system, which includes the amygdala, anterior cingulate, and orbitofrontal cortex. Hostile interpretation bias is likely mediated by amygdala-enhanced detection of threat cues in ambiguous social information. To reverse these associations, IBT uses reinforcement learning against the biased judgments of social threat in ambiguous cues. Notably, we hypothesize that this would engage the orbitofrontal cortex to update the valence-associations of ambiguous information as well as the anterior cingulate cortex during unexpected feedback to perceived threat.

[figure not shown]

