The assessment uses “prototypical” male happy or angry expressions. These were created combining twenty males from the Karolinska Directed Emotional Faces set. Thirteen linear morphs between these expressions generated a set of 15 stimuli, or “morphs,” on a continuum from happy (morph 1) to angry (morph 15). All trials consist of a fixation cross (1000ms plus 500-6000ms jitter, mean 1500 ms), morph presentation (150 ms), visual noise mask (250 ms), and response screen with a question mark (until response). Participants respond via keypress with “angry” or “happy.” Each morph of the full set is presented three times in random order. Data from this assessment is used to estimate each participant’s balance point, or the point along the morph continuum where the participant’s judgments change from predominantly happy to angry.

The training is divided into six blocks. Timing and stimulus presentation are the same as in the assessment block except that feedback was provided after each response. Because some will train during fMRI, which does not allow indefinite timing, the response screen timing is 1500 ms plus 500-6000 ms jitter, mean 2000 ms. Feedback will be presented for 1500 ms. Active training is designed to shift the balance point (measured by a pretraining assessment) toward happy judgments of ambiguous faces. Participants receive positive feedback for rating as happy (and negative feedback for rating as angry) two ambiguous morphs nearest to the balance point and had been rated as angry by the participant during the assessment. Patients will receive encouragement to attend for nonresponses, which are anticipated to be rare. Similarly, sham training provided feedback based on the balance point measured at the beginning of each session during the pretraining assessment block. In the case of sham training, the feedback is designed to reinforce, rather than shift, the current balance point. Regardless of what the baseline balance point is, feedback never encourages incongruent judgments of the three extremes on each end of the morph continuum. Both conditions present each morph twice in random order during each training block. There are six training blocks, consisting of 30 trials each lasting 2.7 minutes. In the scanner, each block will begin with an additional 9.2s of fixation for pre-magnetization and end with an additional 12s of fixation to measure BOLD return to baseline.

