#### **F. Data Analysis Plan:**

Development of Computational Models. The application of computational models of learning to behavior and neural response is integral to both the training and scientific aims of this proposal. We will apply well-established models of human reinforcement learning (variants of Rescorla-Wagner and Pierce-Hall that incorporate stimulus generalization) and assess their fit to IBT data. Goodness of fit will be assessed with expectation-maximization and maximum-likelihood algorithms. Models will also be tested in secondary analyses of IBT data of youths with DMDD from [name] lab. The parameters for the model will be (a) parameters determining initial value, i.e. probability of angry, for each stimulus, (b) learning rate, (c) a parameter determining degree of generalization among stimuli, (d) reliability of judgments (inverse choice temperature). Simulation of the model under parameters estimated from the data will yield predictions for the trialwise likelihood that each face is considered angry and of the trialwise prediction error. (Note: these last two variables could be used as predictors in the fMRI analysis.) For transparency, analytic code (not any data) for all models will be posted to online software development repositories.

Hypothesis Testing. To maintain rigor, all analyses will involve omnibus models with appropriate diagnostics for model fit and influential data. Minimization procedures should ensure balance on the environmental and biological factors (sex, age, SES, and IQ) that may influence hypothesized associations. Additional potential factors are anxiety, depression, pubertal development, and in- or out-of-scanner training. The effects of all of these factors on independent variables will be assessed. If an imbalance across training groups occurs in any of these factors or a significant association is detected between these factors and an independent variable, it will be entered into the omnibus model as a covariate.

Hypothesis 1.1: Baseline hostile interpretation bias is associated with baseline irritability. Linear regression with pre-training balance point (interpretation bias) as a dependent variable and pre-training ARI (irritability) as an independent variable.

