Hypothesis 1.2: Active but not sham, IBT will reduce hostile interpretation bias. Mixed-effects linear regression with balance point (interpretation bias) as a dependent variable and training condition (active vs. sham), and time of interpretation bias assessment (pre- or post-training) as independent variables of interest and person as a grouping variable and random effect. Similar models will test for group differences in active or sham IBT on other measures of hostile interpretation bias after training.

Hypothesis 2.1: The rate of learning new associations to ambiguous faces training will be associated with baseline irritability. For those in the active condition, linear regression will test the association between pre-training ARI (irritability) and learning rate to reversal feedback of baseline angry judgments to the two ambiguous morphs.

Hypotheses 2.2 and 2.3: Active, but not sham, IBT will evoke greater neural response in threat-learning systems. For each person, learning will be modeled with regressors coding the “value” or trialwise likelihood that a participant considers the morph to be angry. The amplitude of BOLD %signal change (activity) or amygdala covariance (generalized psychophysiological interaction; connectivity) related to these regressors represents neural response to value. Critically, these regressors represent learning itself where value is changing towards benign judgments in the active training condition to two ambiguous morphs. These will be carried forward to the second level mixed-effects linear models of the effects of morph by pre-training ARI by training condition. A voxel-wise threshold of  $p < .001$ , whole-brain, cluster corrected to  $p < .05$  via permutation testing or Monte Carlo simulation as appropriate, will be used to identify significant associations. A three-way interaction of change in value by morph by training condition will indicate neural areas where learning is influenced by irritability in active but not sham training of reversals of ambiguous morphs. In addition, our *a priori* identification of the likely role of the amygdala, OFC, and ACC justifies follow-up region-of-interest analyses of mean activity or connectivity extracted from these areas with the same omnibus mixed-effects model.

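### At the two trained morphs, value and error feedback are paired in opposite directions in active and sham, so without a feedback-valence term a pure error response can appear as a value-by-morph-by-condition effect

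*Combined protocol and SAP*

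**What the plan says.** The paragraph on the interpretation bias training session sets the feedback rules. In active training, "Participants receive positive feedback for rating as happy (and negative feedback for rating as angry) two ambiguous morphs nearest to the balance point", these being faces the participant had called angry at the pre-training assessment. For sham, "In the case of sham training, the feedback is designed to reinforce, rather than shift, the current balance point". In both arms, "feedback never encourages incongruent judgments of the three extremes on each end of the morph continuum".

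Section F (Data Analysis Plan), Hypotheses 2.2 and 2.3, defines value as the "trialwise likelihood that a participant considers the morph to be angry". It states that the BOLD amplitude or amygdala covariance "related to these regressors represents neural response to value", treats these regressors as learning itself, and carries them into second-level models of morph, pre-training ARI and training condition. The active-not-sham contrast is part of the stated hypothesis, and the interaction singled out for interpretation is change in value by morph by condition.

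No feedback, outcome or prediction-error regressor is named for this test. The computational-models paragraph of the same section derives trialwise value and prediction error and notes that "these last two variables could be used as predictors in the fMRI analysis". The imaging acquisition paragraph says task events will be modelled but does not list them. Section II expects involvement of the "anterior cingulate cortex during unexpected feedback to perceived threat", and the anterior cingulate is one of the a priori regions of interest.

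**The concern.** The condition contrast is meant to isolate neural response to changing value. At the trained morphs, however, the arms also differ in how value relates to being told wrong. A region that tracks only error feedback, and not value, would have a positive value amplitude in active and a negative one in sham. That difference would be reported as value learning. The risk is not remote, because on the plan's own account the anterior cingulate should respond to unexpected feedback. Exploratory Hypothesis 3.2 reuses value-associated activity and connectivity in the same regions, so any mislabelling would carry over.

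**Working it through.** **1. The plan's own figures.** A trial lasts 1.5 (fixation) + 0.15 (face) + 0.25 (mask) + 2.0 (response screen) + 1.5 (feedback) = 5.4 s. Thirty trials take 162 s = 2.7 min, as stated. The imaging sample also reproduces: r = √.15 = .387, and N = ((1.960 + 0.842)/atanh(.387))² + 3 = 50.0. Neither figure is in dispute, and power does not bear on what the amplitude measures.

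**2. Timing.** From face onset to feedback is 0.15 + 0.25 + 2.0 = 2.4 s at the stated means, about one TR (2.3 s), so the two haemodynamic responses overlap. The 2.7-minute block fits only if the listed means are totals. Those means equal the minima (1000 + 500 = 1500 ms; 1500 + 500 = 2000 ms), which leaves effectively no jitter. If the means describe jitter alone, a trial lasts 7.9 s, a block 3.95 min, and the gap is 3.9 s.

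**3. Extent.** Each morph appears 2 × 6 = 12 times, so the two trained morphs take 24 of 15 × 12 = 180 trials (13%).

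**4. Direction.** Let v be the probability of an angry judgment at a trained morph.
- Active: angry is wrong, so Pr(wrong | v) = v, slope +1.
- Sham: angry is right (inferred from the sham rule), so Pr(wrong | v) = 1 − v, slope −1.

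This follows from the feedback rules alone.

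**5. Strength of the pairing at the trained morphs.** Rescorla-Wagner updating over 12 presentations of each morph, with assumed starting values 0.6 and 0.8:

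| Learning rate (assumed) | Correlation of value with wrong: active | Sham | Wrong of 24: active | Sham |
|---|---|---|---|---|
| .05 | +.24 | −.21 | 12.8 | 5.5 |
| .15 | +.40 | −.28 | 7.9 | 3.4 |
| .30 | +.54 | −.36 | 4.6 | 2.0 |

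**6. Consequence for the test.** Simulated trials of 25 v 25 had 180 task trials per person, TR 2.3 s and a gamma response. The signal reacted to wrong feedback only, with no true value response. Assumed: balance point mean 7.5 (SD 1.2), learning rate .05 to .30, inverse temperature 4 to 8, noise SD 0.15 (60 simulated trials per setting) or 1.0 (200 per setting), and region-level p < .05. Where jitter was included, it was exponential with added means of 1.0 s (fixation) and 1.5 s (response screen). At the trained morphs the value-wrong correlation was +.49 in active and −.23 in sham, with wrong rates of 32% and 12%. On the other 13 morphs the correlation was about −.02 and the wrong rate 7% in both arms.

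Rejection rates, without → with feedback-onset and wrong-feedback regressors:

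| Term | No jitter | Jitter | No jitter, higher noise |
|---|---|---|---|
| Value × morph × condition | 97% → 5% | 47% → 5% | 23% → 4% |
| Morph × ARI × condition, reactivity unrelated to ARI | 2% → 7% | 8% → 8% | 8% → 7% |
| Morph × ARI × condition, reactivity changing 50% per SD of ARI | 33% → 7% | 18% → 8% | 10% → not run |

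With 60 simulated trials, the Monte Carlo standard error of a 47% rate is √(.47 × .53/60) = 6 points.

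**7. What removes it.** An unsplit feedback event left the spurious amplitudes essentially unchanged. A correct/incorrect modulator brought them to 0.00 in both arms. Signed prediction error does not do this. With deterministic feedback it equals 0 − v in active and 1 − v in sham at the trained morphs, so it falls with v at slope −1 in both arms and cannot absorb a pairing that reverses by arm. In simulation (learning rate 0.1, judgment slope 1.5 morphs), adding feedback onset and signed prediction error moved the sham amplitude from −1.01 to −1.05 without jitter and from −0.66 to −0.75 with it (unit: the voxel's feedback response).

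**The case against.** The strongest reply is that the plan is silent on feedback modelling and does not exclude it. Feedback is a task event, and prediction error is already computed and mentioned as a possible imaging predictor. That stands in part: this is a gap in specification, and a reader who inferred that the plan commits to a model without feedback would go too far. But neither statement commits to feedback valence. An onset alone does not help, and signed prediction error leaves the artefact in sham.

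A reader might also infer that the irritability finding could come entirely from reactions to being told wrong. The documents do not support that. Hypotheses 2.2 and 2.3 concern association with irritability, and a condition-wide artefact is not an ARI effect. The simulated ARI interaction stayed at 2% to 8% unless error reactivity was made to depend on ARI. The 50% per SD used for that is an assumption with no counterpart in the documents.

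It is likewise tempting to say that Aim 2 would name the wrong target. Aim 2 concerns the ability to learn benign judgments, and section II places the response to unexpected feedback within that learning system. What is at risk is the narrower reading of the amplitude as response to value.

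Finally, the reversal covers only two of 15 morphs. That is correct, but they are the two whose changing value the plan equates with learning.

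**Conclusion.** The concern holds for the value-by-morph-by-condition effect. As written, section F does not ensure that this effect can be told apart from an arm difference in error feedback at the two trained morphs. The opposite signs follow from the feedback rules, with the sham rule at those morphs inferred from its stated purpose.

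The size rests on assumptions. Across simulations the spurious amplitude ran from +0.43 to +2.3 in active and from −0.28 to −2.2 in sham, in units of the voxel's feedback response, varying with learning rate, judgment slope and jitter. It is larger if the 2.7-minute block is taken at face value, because there is then effectively no jitter. The rejection rates depend equally on the assumed noise.

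The morph × ARI × condition test is affected only if reactivity to negative feedback varies with irritability; otherwise it stays near nominal. The simulations covered activity. The extension to connectivity is by the same reasoning and was not simulated.

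**What to change.** In section F, under Hypotheses 2.2 and 2.3, prespecify for the first-level activity and gPPI models a feedback-onset event and a correct/incorrect feedback modulator. Carry forward only the value amplitude estimated net of these, including into Hypothesis 3.2. Do not list signed prediction error as an alternative. Separately, reconcile the trial timing with the stated block length, since the separation of face and feedback depends on it.

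The cost is about one sentence in the plan and one or two regressors, using feedback the task itself delivers, with no added participants. The standard error of the value amplitude rose by about 2% or less in most settings and by 2.5% at most, without jitter.

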### **I. Hypotheses and Specific Aims:**

Chronic irritability is a prominent dimension of pediatric psychopathology for which evidence-based treatments are scarce, have limited efficacy, or adverse side effects. There is a need to develop novel treatments, especially those that target the neurocognitive basis of irritability. One candidate is Interpretation Bias Training (IBT), a computer-based training designed to target rapid, automatic processing of social information. In a small open trial, IBT showed promise as an acceptable, feasible treatment for irritability. However, its underlying neurocognitive targets have not been established. In order to translate IBT for clinical use, we propose to examine two promising neurocognitive targets of IBT.

**Specific Aim 1:** Establish hostile interpretation bias as a treatment target for irritability and engage it through interpretation bias training. One hundred adolescents, drawn from an outpatient psychiatric clinic with varying degrees of clinically significant irritability, will be randomized to a session of active (n=50) or sham (n=50) IBT.

Hypothesis 1.1: The degree of hostile interpretation bias is positively associated with clinical irritability

Hypothesis 1.2: Active but not sham interpretation bias training will reduce hostile interpretation bias.

**Specific Aim 2:** Establish the ability to learn benign judgments of ambiguously hostile social information as a treatment target for irritability and engage it through interpretation bias training. A subsample of 50 participants (n=25 in each active and sham group) will train during fMRI.

Hypothesis 2.1: Learning rates during active IBT will be associated with baseline irritability.

Hypotheses 2.2, 2.3: In neural systems underlying threat learning, response while learning new associations during active IBT will be related to clinical irritability in terms of both neural activity (2.2) and functional connectivity (2.3).

[figure not shown]
**Exploratory Aim 3:** Provide preliminary evidence that changes in treatment targets are related to changes in irritability. To better establish the mechanism of target engagement and gather preliminary evidence for an efficacy trial, we will measure any changes in irritability after IBT. Therefore, we hypothesize that changes in irritability following active IBT will be associated with changes in hostile interpretation bias (hypothesis 3.1) and threat system response (hypothesis 3.2).

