#### **E. Potential Scientific Problems:**

This study is designed to assess the targets of IBT for the treatment of clinically significant irritability in patients, i.e. we are testing the association between the targets and severity of irritability within clinically irritable patients. This study does not include a group of non-irritable patients. The mechanism of IBT's effect on irritability is unknown. While the training is designed to target hostile interpretation bias via reinforcement learning, the training may work through alternative means. For example, youths with severe, chronic irritability have deficits in labeling face-emotions. The training may work through increasing emotion recognition; such training has been proposed to treat irritability. In this case, this study will generate measures of reliability and neural response for future investigations. Indeed, procedures for exploratory Aim 3 will gather preliminary evidence of efficacy.

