Exploratory Hypothesis 3.1: Change in irritability after training is associated with change in hostile interpretation bias. We will investigate this relationship with mixed-effects linear models with ARI (irritability), balance-point (interpretation bias), and time of assessment (pre- or post-training) as within-person variables.

Exploratory Hypothesis 3.2: Change in irritability after training is associated with magnitude of neural threat-learning system response. We will investigate this relationship with mixed-effects linear models with ARI (irritability), mean value-associated connectivity or activity in the amygdala, OFC, and ACC, and time of assessment (pre- or post-training) as within-person variables.

As requested by NIMH scientific review, I will conduct two additional, secondary analyses: 1) a mediation analysis of active IBT on change in irritability and 2) a multivariate analysis of the shared and unique effects of irritability, anxiety, and depression on hostile interpretation bias.

Power analysis. For Aim 1, a sample size of 100 achieves 80% power to detect an effect size of the expected association of at least  $r = .25$  between baseline hostile interpretation bias and baseline irritability using Pearson correlation at a one-tailed alpha of .05. Thus, the proposed study will have sufficient power to detect small to medium sized interaction effects. The study is overpowered for detecting expected effects of IBT on hostile interpretation bias which should be large. For Aim 2, a sample size of 100 likewise achieves more than 80% power to detect the expected large association between baseline irritability and learning. For imaging, using a medium effect size of a term in a general linear model ( $R^2 = .15$ ), the required sample for 80% power is 50 individuals ( $p = .05$ ). Our previous study that examined IBT-related changes to face-emotions was medium to large in the orbitofrontal cortex. Thus, the proposed study will have sufficient power to detect small to medium sized interaction effects. Aim 3 is exploratory; this study may estimate effect sizes for future research.

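### Hypotheses 2.2 and 2.3: the interaction named as showing an irritability effect leaves out ARI, although the fitted model contains it

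*Combined protocol and SAP*

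**What the plan says.** The relevant statements in the combined protocol and SAP are these.

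- **Aim 2 (section I).** Neural response during active training "will be related to clinical irritability in terms of both neural activity (2.2) and functional connectivity (2.3"). Under Outcome Measures, irritability is measured dimensionally by the ARI.
- **Hypothesis statement (section F, hypotheses 2.2 and 2.3).** "Active, but not sham, IBT will evoke greater neural response in threat-learning systems". Irritability is not mentioned.
- **First level.** Value is a trial-by-trial regressor for how likely the participant is to judge the face angry. The activity or connectivity amplitude "related to these regressors represents neural response to value".
- **Second level.** These amplitudes go into "second level mixed-effects linear models of the effects of morph by pre-training ARI by training condition".
- **Deciding term.** "A three-way interaction of change in value by morph by training condition will indicate neural areas where learning is influenced by irritability", with the rest of the sentence restricting this to active and not sham training.
- **Region-of-interest step (amygdala, OFC, ACC).** "follow-up region-of-interest analyses of mean activity or connectivity extracted from these areas with the same omnibus mixed-effects model".
- **Power analysis.** The imaging sample of 50 is justified "using a medium effect size of a term in a general linear model", with R² = .15. The term is not named.
- **Exploratory hypothesis 3.2.** ARI, mean value-related neural response and pre/post time are listed together as within-person variables. The Training, Visit 2 section describes one training session, in the scanner for the imaging arms, with laptop bias assessments outside the scanner before and after it.

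**The concern.** One paragraph gives two different accounts of what decides hypotheses 2.2 and 2.3. The fitted model has an irritability term. The interpretation sentence relies on a term without one, yet draws a conclusion about irritability from it. The hypothesis statement at the head of the paragraph is worded as an active-versus-sham difference, so it fits the term without ARI. Aim 2 is worded as an association with irritability, so it fits the term with ARI.

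If the sentence were followed literally, a region that merely responds differently under active and sham training could be reported as one where irritability shapes learning. Aim 2 is not labelled exploratory, and section G presents learning-circuitry response as one of two targets supporting a later go/no-go efficacy trial. The same section also calls the project hypothesis-generating, which tempers the stakes without removing them.

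**Working it through.** **1. The plan's own figure.** The nearest number is the imaging sample of 50 for 80% power at R² = .15, p = .05.

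- Fisher z, two-sided: r = √.15 = .387, atanh(r) = .4086, N = ((1.960 + 0.842)/.4086)² + 3 ≈ 50.01, rounded up to 51.
- Noncentral F, one-df term, three predictors: f² = .15/.85 = .1765, λ = .1765 × 50 = 8.82, power .83 at N = 50. The smallest N reaching 80% is 47.

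The stated 50 is reproduced closely. It applies to any single term, so it does not show which interaction was meant.

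**2. The two terms side by side.**

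| Source in section F | Components |
|---|---|
| Second-level model | morph, pre-training ARI, training condition |
| Interaction named as deciding | change in value, morph, training condition |

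ARI appears only in the first. Value is defined as the likelihood of an angry judgment, so it does not stand in for ARI.

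**3. What the named term tests.** Let y be the second-level outcome (value-related amplitude), M morph, A centred ARI and C condition. The model's interactions are MA, MC, AC and MAC. Reduce morph to a per-person contrast D, reversed minus other morphs:

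D = b_M + b_MA·A + b_MC·C + b_MAC·A·C + error

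Value is already in y, so value × morph × condition corresponds to b_MC, the average active-minus-sham difference in D. Irritability acting in active but not sham training corresponds to b_MAC, the difference between arms in the slope of D on ARI. Either can be zero when the other is not. The count of factors shows the same mismatch. If value is not counted, the named term is two-way. If value is counted, the irritability term is four-way.

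**4. Illustration.** Inputs: 25 per arm (Aim 2), two-sided alpha .05, 4,000 simulated trials, and D regressed on C, A and A × C. The effect is an assumption: 0.85 SD, close to d = 2√.1765 = 0.84, which is what R² = .15 would mean for a two-arm difference.

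| Truth assumed | Morph × condition significant | Morph × ARI × condition significant |
|---|---|---|
| Training effect only, ARI irrelevant | 82.8% | 5.1% |
| ARI-dependent effect only | 5.2% | 81.3% |
| Neither | 5.0% | 5.3% |

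The table shows that the two terms answer different questions. The 82.8% is simply the power of an active-sham contrast for an effect assumed to be present.

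**5. Hypothesis 3.2.** With one neural summary N per person, the within-person deviation of N is zero. In a mixed model with a random person intercept,

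ARI = b0 + b1·T + b2·N + b3·N·T + u + error,

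the expected pre-to-post change (T from 0 to 1) is b1 + b3·N. The main effect b2 can be estimated but cancels out of the change. Only b3 relates neural response to change in ARI.

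**The case against.** The strongest reply is that the intended meaning can be recovered. The declared second-level model has exactly one three-way interaction, and it contains ARI. The sentence's own conclusion names irritability, condition and morph. The phrase about change in value can be read as describing the outcome. The region-of-interest step reuses the same model, and section E says "we are testing the association between the targets and severity of irritability within clinically irritable patients". This largely stands: ARI was probably intended. It does not settle the matter, because the hypothesis statement in the same paragraph also leaves irritability out and no other section reconciles it with Aim 2.

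A second reply is that the simulation says little about the plan. This also stands:

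- The R² = .15 belongs to an unnamed term.
- No alpha is given for the region-of-interest step.
- The whole-brain rule is voxel-wise p < .001 with cluster correction to p < .05, which was not simulated.
- Reducing 15 morphs to one contrast is a simplification made here.

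A reader might infer that the plan never tests irritability in the imaging data, or that it carries an 83% false-positive rate. The documents support neither. The ARI term is in the fitted model and would be estimated, and the 83% depends on an assumed training effect and a literal reading of one sentence.

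On hypothesis 3.2, a reader might infer that the model cannot be fitted. That would be so for a person-constant main effect alongside fixed person effects, but the plan specifies mixed-effects models.

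**Conclusion.** The interpretation rule for hypotheses 2.2 and 2.3 is wrong as written, probably through a drafting slip. The named interaction is in effect morph by condition and cannot show that irritability influences learning. The risk is mislabelling or selective emphasis: two terms could each be defended afterwards as the deciding one. It is not a failure to run the right test. This conclusion rests on comparing the sentences and on value-related response being the second-level outcome; it does not depend on the simulation. The sample size, data and fitted model are unaffected.

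The hypothesis 3.2 point is minor and belongs to an exploratory aim. Neural response is obtained from one training session, so it has no pre- and post-training values, and its main effect does not address change in ARI.

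**What to change.** - State that hypotheses 2.2 and 2.3 are decided by the morph × pre-training ARI × training condition term, on value-related activity (2.2) or connectivity (2.3), both voxel-wise and in the amygdala, OFC and ACC regions.
- Report morph × condition separately, labelled as a training effect.
- Reword the section F hypothesis statement to agree with Aim 2.
- For exploratory hypothesis 3.2, enter neural response as a between-person covariate and test neural response × time, or regress post-training ARI on pre-training ARI and neural response.

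The first three changes cost wording only, since the model already holds the ARI term. The fourth changes one exploratory model specification. No new data are needed, and the changes should be made before the imaging results are examined.
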